6. TREATMENT PLAN

Patients will be enrolled into successive dosage level cohorts of 3 or 6 patients and monitored for dose-limiting toxicity (DLT).

DLT (Based on NCI CTCAE version 4.0) is defined as any Grade 2, 3 or 4 immediate hypersensitivity reactions, Grade 3 or 4 fever that may possibly be associated with the immunization, Grade ≥ 2 autoimmune events except for vitiligo or fever for less than 2 days and less than 101.5 °F, Grade ≥ 2 allergic reactions (grade 2 is defined as generalized urticaria as defined by CTCAE version 4.0), or Grade ≥ 3 non-hematologic toxicity.

During dose escalation through the first three patients of cohort 3, there will be a minimum of 1 week between enrolling successive patients. The first patient will be called to check on their condition prior to enrolling the second patient since patients can be enrolled after 1 week of initiation of cohort 3. If no DLT have been observed at this point, then further enrollment can occur in cohort 3 and phase II component (Cohort 4) without the 1-week waiting period. Between dosage levels, through Cohort 3, assessment of DLT for dose escalation will be made after all patients in a cohort have had a study visit at least 3 weeks after receiving their first dose of vaccine and all the available safety data and laboratory results have been reviewed. Patients in cohort 5 may begin injections once all patients in cohort 4 have had at least their first injections and all patients in cohort 3 have had a study visit at least 3 weeks after receiving their first dose of vaccine. If DLT occurs in $<33\%$ of patients in a given dosage level cohort, progression to the next dosage level will proceed. If DLT occurs in $\geq 33\%$ of patients in a given cohort, the next lower dosage level will be defined as the maximum tolerated dose (MTD). If DLT occurs in $<33\%$ of patients in the highest dosage level tested, that dosage level will be defined as the MTD. In phase II (Cohort 4) and Cohort 5, if at any time the rate of DLT in patients enrolled is $\geq 33\%$, the MTD will be re-defined as the next lower dosage level. Additional details of this dose escalation and de-escalation plan are provided below and in Figures 3A, 3B and Table 3.

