- 1) Phase I: Cohort 1: Three patients will receive Ad5 [E1-, E2b-]-CEA(6D) at a dose of 1×10^9 particles in 0.5 mL subcutaneously (SQ) in the same thigh every 3 weeks for 3 immunizations. Immunizations should be separated by 5 cm. A diary card will be given to each subject at the first treatment along with a ruler to record any adverse reactions for 2 days after treatment (24 hours and 48 hours post injection). The diary card will be placed in the study file. Assessment of DLT for dose escalation will be made after all patients in this cohort have had a study visit at least 3 weeks after receiving their first dose of vaccine. If there are no DLT (as defined above), then patients may begin enrolling into cohort 2. If there is 1 DLT then an additional 3 patients will be enrolled at this dosage level. Assessment of DLT for dose escalation will be made after the 3 additional patients have had a study visit at least 3 weeks after receiving their first dose of vaccine. If none of these latter 3 patients have DLT, then patients may begin enrolling into cohort 2. If 2 patients have DLT at this lowest dosage level, dosing will be de-escalated to 1×10^8 particles and a new cohort of 3 patients instituted.
- 2) Cohort 2: Three patients will receive Ad5 [E1-, E2b-]-CEA(6D) at a dose of 1×10^{10} particles in 0.5 mL SQ in the same thigh every 3 weeks for 3 immunizations. Immunizations site should be separated by 5 cm. A diary card will be given to each subject at the first treatment along with a ruler to record any adverse reactions for 2 days after treatment (24 hours and 48 hours post injection). The diary card will be placed in the study file. Assessment of DLT for dose escalation will be made after all patients in this cohort have had a study visit at least 3 weeks after receiving their first dose of vaccine. If there are no DLT, then patients may begin enrolling into cohort 3. If there is 1 DLT then an additional 3 patients will be enrolled at this dosage level. Assessment of DLT for dose escalation will be made after the 3 additional patients have had a study visit at least 3 weeks after receiving their first dose of vaccine. If none of these latter 3 patients have DLT, then patients may begin enrolling into cohort 3. If 2 patients have DLT at this dosage level, the dosage level in cohort 1 will be considered the MTD. If only 3 patients were enrolled in cohort 1, an additional 3 patients will be enrolled at that dosage before proceeding to the next cohort.

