- 3) Cohort 3: Six patients will receive Ad5 [E1-, E2b-]-CEA(6D) at a dose of 1×10^{11} particles in 0.5 mL SQ in the same thigh every 3 weeks for 3 immunizations. Immunizations site should be separated by 5 cm. A diary card will be given to each subject at the first treatment along with a ruler to record any adverse reactions for 2 days after treatment (24 hours and 48 hours post injection). The diary card will be placed in the study file. Assessment of DLT for proceeding to phase II enrollment (Cohort 4) will be made after all patients in this cohort have had a study visit at least 3 weeks after receiving their first dose of vaccine. If there is 0 or 1 DLT, then subjects may enroll in Cohort 4. If 2 patients have DLT at this dosage level, the dosage level in cohort 2 will be considered the MTD. If only 3 patients were enrolled in cohort 2, an additional 3 patients will be enrolled at that dosage before proceeding to the next level.
- 4) Phase II cohort (Cohort 4): After the MTD is established, an additional 12 patients will receive Ad5 [E1-, E2b-]-CEA(6D) at the MTD every 3 weeks for 3 immunizations.

Note: if during accrual of patients in the phase II cohort, DLT occurs at a sufficient rate such that the rate of DLT amongst the total number of patients (those treated at MTD in phase I and those in phase II) is $\geq 33\%$, then phase II will be restarted at the dosage level which is one level below the prior MTD.

- 5) Cohort 5: Six patients will receive Ad5 [E1-, E2b-]-CEA(6D) at a dose of 5×10^{11} particles SQ in 2.5 mL every 3 weeks for 3 immunizations. Assessment of DLT will be made after all patients in this cohort have had all 3 injections and been observed for at least 30 days after the last injection. If there are 0-1 DLT, then this will be declared the maximum feasible dose. If there are 2 or more DLT, then 1×10^{11} particles will be declared the MTD.

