- 6) Cohort 6: Up to ten (10) patients will receive Ad5 [E1-, E2b-]-CEA(6D) at a dose of 5×10^{11} particles SQ in 1.0 mL every 3 weeks for 3 immunizations. Patients will be permitted to receive booster doses of Ad5 [E1-, E2b-]-CEA(6D) every 3 months for a period of two years following the first 3 treatments. In the event that a qualified patient undergoes reimaging prior to the completion of their initial 3 study immunizations and is found to have disease progression, the patient should continue on the immunization protocol because this could be a “flare reaction” associated with the vaccine which may be an inflammatory response. Patients will be required to have MRI/CT scans performed prior to initiation of treatment, at 3 month intervals +/- 1 month for 12 months or if the investigator believes signs or symptoms are suggestive of progression or relapse. All patients will be followed for overall survival for a period of 24 months from initiation of treatment.
- 7) Patients will have 90 mL peripheral blood drawn prior to each immunization and approximately 3 weeks after the third immunization (Week 9) to determine whether there is an effect on the immune response at specific time points during the study and/or after a specific number of immunizations.
- 8) Time to progression will be measured using CT scans performed at approximately 3 month intervals (based on clinical standard of care).
- 9) For all patients, if scheduling conflicts arise, the scheduled 3-week interval between immunizations may be modified so that the interval between immunizations is between 20 and 28 days (3 weeks -1 day to 3 weeks +7 days). If the second and/or third immunization is delayed, the subsequent immunizations should occur no earlier than 20 days after the previous immunization.
- 10) The following safety events will trigger a temporary suspension of study vaccinations:
 - a) If one or more patients develop a Grade 4 allergic reaction without a clear attributable cause, other than study vaccine
 - b) Death not attributed to disease.

Assessment of these halting rules is a review of cumulative events for all study participants, and should not be confused with reasons for delaying or terminating the immunization schedule of any individual patient.

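### Cohort 6 can open at 5×10^11 particles without waiting for, or depending on, the DLT result of cohort 5 at the same particle dose; separately, the de-escalation endings of items 2 and 3 in section 6 need a text correction

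*Combined protocol and SAP*

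**What the plan says.** The file holds several protocol versions. I take the one containing cohort 6 as current; that order is inferred from content.

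**Cohort 6.** Section 6, item 6: "Up to ten (10) patients will receive" 5×10^11 particles in 1.0 mL, three times at three-week intervals, with boosters permitted afterwards. The Protocol Summary repeats the dose and cohort size. Neither place makes entry depend on toxicity or on cohort 5.

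**Cohort 5.** Item 5 gives six patients 5×10^11 in 2.5 mL. DLT are assessed once all have had three injections and at least 30 days of observation. With 0–1 DLT this is the maximum feasible dose. With two or more, 1×10^11 "particles will be declared the MTD". Its entry sentence in the opening text of section 6 concerns timing: "Patients in cohort 5 may begin injections once all patients in cohort 4 have had at least their first injections", plus a three-week visit for cohort 3.

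**General rules in the opening text of section 6.** If fewer than 33% of a cohort have DLT, "progression to the next dosage level will proceed". At 33% or more, the next lower level is defined as the MTD. A continuous clause follows: "In phase II (Cohort 4) and Cohort 5, if at any time the rate of DLT in patients enrolled is" at least 33%, the MTD is re-defined one level down.

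**De-escalation in items 2 and 3.** After 2 DLT the level below becomes the MTD. If only three patients were treated there, item 2 says "an additional 3 patients will be enrolled at that dosage before proceeding to the next cohort" and item 3 says "an additional 3 patients will be enrolled at that dosage before proceeding to the next level". Item 4 then reads: "After the MTD is established, an additional 12 patients will receive" vaccine at the MTD.

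**The concern.** Safety is the primary objective, and the rule for what happens after a dose fails should be readable without inference. Cohort 6 repeats the particle dose of cohort 5, so the cohort 5 result is the direct evidence on whether cohort 6 should be treated. The text does not connect the two. Followed literally, cohort 6 could enrol before cohort 5 has been assessed, or after cohort 5 has failed its own criterion.

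The wording in items 2 and 3 is a lesser matter of the same kind. The cohort after cohort 2 is cohort 3, at ten times the dose just rejected, and the dosage level above cohort 3 is 5×10^11. Neither can be the intended destination once a lower MTD has been declared.

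**Working it through.** **1. The plan's own threshold.** Section 8.1 calls a level safe at 0 of 3, ≤1 of 6, ≤3 of 12 or ≤5 of 18. These are 0%, 16.7%, 25.0% and 27.8%, all below 33%. One more DLT gives 1/3, 2/6, 4/12 or 6/18, each 33.3%. The threshold reproduces, and for six patients it agrees with item 5: two DLT reject the dose.

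**2. Suppose cohort 5 ends with 2 DLT in 6. What keeps cohort 6 closed?**

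- *Item 5* makes 1×10^11 the MTD. Item 6 is not written in terms of the MTD and stays at 5×10^11.
- *The under-33% gate* governs moving to another dosage level. Section 6.2.1 gives cohorts 5 and 6 the same 5×10^11 particles, so cohort 6 is not a next level.
- *The continuous clause* names cohorts 4 and 5 only. Where it applies, it re-defines the MTD without saying that enrolment stops.
- *Section 8.1* would not call 5×10^11 safe, but attaches no enrolment consequence to that.
- *Halting and stopping rules* concern Grade 4 allergic reactions, deaths, and two patients with related Grade 4 toxicity. DLT also include Grade 2 allergic and autoimmune events and Grade 3 non-hematologic toxicity. A dose can therefore fail on DLT without triggering them.

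**3. Table 3.** Its limits are 1, 2, 4, 8, 10 and 13 DLT for cohorts of 3, 3, 6, 12, 6 and 10.

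- *Read per cohort*, 10 of 6 and 13 of 10 are impossible. The smallest counts reaching 33% are 2 of 6 (33.3%) and 4 of 10 (40%).
- *Read cumulatively*, enrolment is 3, 6, 12, 24, 30 and 40, so 10/30 = 33.3% and 13/40 = 32.5%. This appears to be how the figures arose. But it pools dose levels: 2 DLT in cohort 5 with none before is 2/30 = 6.7%, nowhere near the limit of 10.

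Either way the table does not detect failure at 5×10^11.

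**4. How often cohort 5 would reject the dose.** The documents give no DLT rate, so the true rate p is an assumption.

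P(≥2 of 6) = 1 − (1−p)^6 − 6p(1−p)^5

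| Assumed p | (1−p)^6 | 6p(1−p)^5 | P(reject) |
|---|---|---|---|
| 5% | 0.735 | 0.232 | 0.033 |
| 10% | 0.531 | 0.354 | 0.114 |
| 20% | 0.262 | 0.393 | 0.345 |
| 30% | 0.118 | 0.303 | 0.580 |

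These are chances that the gap becomes relevant, not chances of harm or of cohort 6 actually being opened.

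**5. Exposure if it did open.** 10 patients × 3 = 30 primary immunizations, with boosters in addition.

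**6. Items 2 and 3.** Set beside item 4, which places Cohort 4 at the MTD, and beside the under-33% gate, the only consistent destination after topping up to six patients is phase II at the MTD just declared. Item 3 itself, earlier in the same paragraph, calls the step after cohort 3 phase II enrolment (Cohort 4).

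**The case against.** The best reply is that the plan taken as a whole already says enough. MTD means the highest dose to be given, so declaring 1×10^11 the MTD implies that 5×10^11 is closed. Section 8.1's definition of a safe level is not limited to particular cohorts, and the general sentence on 33% or more in a given cohort would cover cohort 6's own DLT. The medical monitor and the Principal Investigator make the escalation decision, and the Principal Investigator or sponsor may suspend vaccination on any safety concern. Figures 3A and 3B, which section 6 cites for detail, are not shown. Section 3 is redacted, so any rationale or earlier results for cohort 6 cannot be seen.

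Much of this stands. It makes opening cohort 6 after a failed cohort 5 unlikely in practice, and it limits the finding to the visible text. It does not supply a rule: an implication from the term MTD, a definition without a consequence, and a power to suspend are each weaker than an entry condition. Nothing in the visible text requires cohort 5 to be assessed first.

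A reader might infer three stronger things that the documents do not support:

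- *That items 2 and 3 order dosing at or above a rejected level.* They do not; item 4 and the gate recover the intended route. A version describing four dosage levels also records 1×10^11 as the MTD determined in Phase I, and section 6.2.2 of the current text prepares cohorts 3 and 4 at that dose. If Phase I is complete on that basis, both branches are closed.
- *That cohort 5 may open after 1×10^11 has been rejected.* Its entry sentence sets only timing, but 5×10^11 is a higher level, so the gate applies. The fixed fallback to 1×10^11 would be wrong only on a path that the gate does not allow.
- *That cohort 6 has no safety protection.* The halting rules, the stopping rules and discretionary suspension all apply to it.

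**Conclusion.** The concern holds in a limited form, and it is minor. Item 6 and the Protocol Summary allow up to 10 patients at 5×10^11 with no DLT entry condition and no requirement that cohort 5 be assessed first, and no other visible provision closes the gap. Unlike the item 2 and 3 branches, it is not settled by a completed Phase I, because it depends on what cohort 5 shows. It matters only if cohort 5 rejects the dose, or if cohort 6 starts before that is known. The first has probability of about 3% to 58% over assumed true DLT rates of 5% to 30%. The conclusion rests on the visible text and on the cohort 6 version being current.

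The endings of items 2 and 3 are a text correction only. I attach no size to them, because other sentences supply the answer and the branches are probably closed.

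**What to change.** 1. Add to item 6 and to the Protocol Summary: *Cohort 6 opens only after all cohort 5 patients have been assessed for DLT under item 5 and 0–1 of 6 had DLT. If 2 or more cohort 5 patients have DLT, no further patients are enrolled at 5×10^11.*
2. Name cohort 6 in the continuous DLT clause, and apply the clause only from the second DLT onward. Without that floor, one DLT among the first three patients (1/3 = 33.3%) would trigger it, although item 5 accepts one in six.
3. Close the de-escalation sentences of items 2 and 3 with a move to *phase II (Cohort 4) at that dosage*. If Phase I is complete, record those branches as closed.

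**Cost.** A short amendment and no extra patients. Cohort 6 may have to wait for the cohort 5 assessment. On the nominal schedule that is at least 2×21 + 30 = 72 days after the last cohort 5 patient's first injection.

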	
additional 3 patients will be enrolled at this dosage level. Assessment of DLT for dose escalation will be made after the 3 additional patients have had a study visit at least 3 weeks after receiving their first dose of vaccine. If none of these latter 3 patients have DLT (i.e., 1 DLT in the 6 total patients), then patients may begin enrolling into cohort 2. If 2 patients have DLT at the lowest dosage level, dosing will be de-escalated to 1×10^8 particles.
 
2) Cohort 2: Three patients will receive Ad5 [E1-, E2b-]-CEA(6D) at a dose of 1×10^{10} particles SQ in 0.5 mL every 3 weeks for 3 immunizations. Assessment of DLT for dose escalation will be made after all patients in this cohort have had a study visit at least 3 weeks after receiving their first dose of vaccine. If there are no DLT, then patients may begin enrolling into cohort 3. If there is 1 DLT then an additional 3 patients will be enrolled at this dosage level. Assessment of DLT for dose escalation will be made after the 3 additional patients have had a study visit at least 3 weeks after receiving their first dose of vaccine. If none of these latter 3 patients have DLT, then patients may begin enrolling into cohort 3.
 
3) Cohort 3: Six patients will receive Ad5 [E1-, E2b-]-CEA(6D) at a dose of 1×10^{11} particles SQ in 0.5 mL every 3 weeks for 3 immunizations. Assessment of DLT for proceeding to phase II enrollment will be made after all patients in this cohort have had a study visit at least 3 weeks after receiving their first dose of vaccine. If there is 0 or 1 DLT, then patients may begin enrolling into the phase II portion of the study.
 
4) Phase II Cohort (Cohort 4): An additional 12 patients will receive Ad5 [E1-, E2B-]-CEA(6D) at the MTD every 3 weeks for 3 immunizations.
 
5) Cohort 5: Beginning after the third dose of ETBX-011 for the 12th patient in cohort 4, enrollment in an additional higher dose cohort will be permitted. Six patients will receive Ad5 [E1-, E2b-]-CEA(6D) at a dose of 5×10^{11} particles SQ in 2.5 mL every 3 weeks for 3 immunizations. Assessment of DLT will be made after all patients in this cohort have had all 3 injections and been observed for at least 30 days after the last injection. If there are 0-1 DLT, then this will be declared the maximum feasible dose. If there are 2 or more DLT, then 1×10^{11} particles will be declared the MTD.
 
6) Cohort 6: Up to ten (10) will receive Ad5 [E1-, E2b-]-CEA(6D) at a dose of 5×10^{11} particles SQ in 1.0 mL every 3 weeks for 3 immunizations. Patients will be permitted to receive booster doses of Ad5 [E1-, E2b-]-CEA(6D) every 3 months for a period of one year following the first 3 treatments. In the event that a qualified patient undergoes reimaging prior to the completion of their initial 3 study immunizations and is found to have disease progression, the patient should continue on the immunization protocol because this could be a “flare reaction” associated with the vaccine which may be an inflammatory response. Patients will be required to have MRI/CT scans performed prior to initiation of treatment, at 3 month intervals +/- 1

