Etubics Corporation will fully review all available safety data, consult with the principal investigator, medical monitor and the FDA as needed, before determining if resuming vaccinations is appropriate. If it is determined that study vaccinations can resume, the halting rules will apply to each subsequent event that meets the criteria described above. Vaccinations may also be suspended for safety concerns other than those described above if, in the judgment of the principal investigator or sponsor, participant safety is threatened.

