8. STATISTICAL CONSIDERATIONS

8.1. Safety

We will evaluate safety continuously in a cohort. We will make our overall assessment of whether to escalate to the next dose level at least 3 weeks after the last patient in the previous cohort has received their first injection. This decision will be made by the medical monitor and the Principal Investigator. A note will be generated following the assessment decision and filed in study binder. A dosage level will be considered safe if <33% patients treated at a dose level experience DLT (i.e., 0 of 3, ≤ 1 of 6, ≤ 3 of 12, or ≤ 5 of 18 patients). DLT is defined in Protocol Section 6. Safety will be evaluated in 3 or 6 patients at each dosage level in phase I. Safety will continue to be monitored among additional patients treated at the MTD in phase II. A patient will be considered evaluable for safety if treated with at least one immunization. DLTs will be observed through 9 weeks to accommodate safety evaluation of all 3 product doses.

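### Table 3 of the last protocol version prints wrong ≥33% DLT counts for cohorts 2 to 6 as its columns are labelled, and the readable text does not make cohort 6 conditional on the cohort 5 result

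*Combined protocol and SAP*

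**What the plan says.** All references are to the last protocol version in the combined file, the one that adds cohort 6, unless stated otherwise.

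- **Section 6, opening text.** Escalation is judged within a dosage level cohort against a 33% DLT limit. The section adds: "Additional details of this dose escalation and de-escalation plan are provided below and in Figures 3A, 3B and Table 3".
- **Section 6, running rule.** "In phase II (Cohort 4) and Cohort 5, if at any time the rate of DLT in patients enrolled is" 33% or more, the MTD becomes the next lower level. Cohort 6 is not named.
- **Item 3 (cohort 3, six patients).** "If 2 patients have DLT at this dosage level, the dosage level in cohort 2 will be considered the MTD".
- **Item 5 (cohort 5, six patients at 5×10^11).** "If there are 0-1 DLT, then this will be declared the maximum feasible dose. If there are 2 or more DLT, then" 1×10^11 is declared the MTD.
- **Item 6 (cohort 6).** "Cohort 6: Up to ten (10) patients will receive Ad5 [E1-, E2b-]-CEA(6D) at a dose of" 5×10^11. The Protocol Summary says the same ("Cohort 6: Up to ten (10) will receive Ad5 [E1-, E2b-]-CEA(6D) at a dose of" 5×10^11), and Section 6.2.1 gives boosters at that dose. None of the three refers to the cohort 5 result.
- **Section 8.1.** "A dosage level will be considered safe if <33% patients treated at a dose level experience DLT", spelled out as 0 of 3, at most 1 of 6, 3 of 12 or 5 of 18.
- **Table 3 (Section 6.1).** Columns are headed by cohort, each with its own n (3, 3, 6, 12, 6, 10). The row of counts needed to reach 33% reads 1, 2, 4, 8, 10, 13.

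In the protocol version directly before this one in the file, Table 3 is laid out by number evaluable: 1 for 1–3 patients, 2 for 4–6, 3 for 7–9, 4 for 10–12, 5 for 13–15, 6 for 16–18.

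**The concern.** Safety is the primary objective, and Table 3 is the plan's numeric aid for deciding when a dose has failed. As labelled, it tells the user that cohort 3 reaches the limit at 4 of 6 and cohort 4 at 8 of 12, twice the counts that the text allows. For both cohorts at 5×10^11 it gives numbers that no cohort of that size can produce.

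The second issue lies in the same place. If cohort 5 has 0 or 1 DLT, items 5 and 6 agree. If it has 2 or more, item 5 makes 1×10^11 the MTD while item 6 still assigns up to ten patients to five times that dose, and no readable sentence says what then happens to cohort 6. The automatic halting and stopping rules need a Grade 4 allergic reaction, a death not due to disease or possibly related to the vaccine, or related Grade 4 toxicity in two patients. Two Grade 3 non-hematologic DLT would meet none of them. What remains is discretion: "Vaccinations may also be suspended for safety concerns other than those described above if, in the judgment of the principal investigator or sponsor" sees a threat to participants.

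**Working it through.** **1. Reproduce the plan's own limits.** The smallest count r with r/n ≥ 33% is r = ceil(0.33 × n); the largest safe count is r − 1.

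- n = 3: ceil(0.99) = 1, so 0 is safe.
- n = 6: ceil(1.98) = 2, so at most 1.
- n = 12: ceil(3.96) = 4, so at most 3.
- n = 18: ceil(5.94) = 6, so at most 5.

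These are exactly the Section 8.1 limits. The same formula reproduces the preceding version's Table 3 for every n from 1 to 18.

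**2. Apply it to Table 3 of the last version.**

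| Cohort | n in header | Printed count | Printed / n | Correct count | Running total N | Printed / N |
|---|---|---|---|---|---|---|
| 1 | 3 | 1 | 33.3% | 1 | 3 | 33.3% |
| 2 | 3 | 2 | 66.7% | 1 | 6 | 33.3% |
| 3 | 6 | 4 | 66.7% | 2 | 12 | 33.3% |
| 4 | 12 | 8 | 66.7% | 4 | 24 | 33.3% |
| 5 | 6 | 10 | 166.7% | 2 | 30 | 33.3% |
| 6 | 10 | 13 | 130.0% | 4 | 40 | 32.5% |

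By each column's own n, only cohort 1 is right, and the entries for cohorts 5 and 6 exceed the number of patients.

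**3. Test the running-total reading.** It explains the first five entries. It does not explain the sixth: 0.33 × 40 = 13.2, so 14 are needed (14/40 = 35.0%). It also pools doses from 1×10^9 to 5×10^11. If the 24 patients in cohorts 1 to 4 had no DLT, all six cohort 5 patients could have one and the total would be 6, short of the printed 10, whereas item 5 acts at 2.

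**4. Pooling at one dose level, which is what Section 8.1 describes.**

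- Cohorts 3 and 4, if both are at 1×10^11: n = 6 + 12 = 18, limit 6 (6/18 = 33.3%).
- Cohorts 5 and 6: n = 6 + 10 = 16, ceil(5.28) = 6 (6/16 = 37.5%; 5/16 = 31.3%).

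**5. How often the item 5 / item 6 conflict would arise.** The documents give no DLT rate at 5×10^11, so the rate p is assumed. P(2 or more of 6) = 1 − (1 − p)^6 − 6p(1 − p)^5.

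| Assumed p | P(2 or more of 6) |
|---|---|
| 5% | 0.033 |
| 10% | 0.114 |
| 20% | 0.345 |
| 33% | 0.642 |

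**The case against.** **On the table.** The caption speaks of rates during accrual, and running totals reproduce five of six entries. On that view there is one rounding slip and a labelling fault, and operative text elsewhere gives the right limits: item 5 has 2 of 6 for cohort 5, and the 33% limit in 8.1 implies at most 3 of 10 for cohort 6. It stands that 5×10^11 does have a usable limit outside the table. It does not rescue the table, whose headers show each cohort's own n, whose rule in Sections 6 and 8.1 works per dose level, and whose last entry fails on either reading. For cohorts 1 to 3 the practical effect may be small, since the preceding version's Summary already records 1×10^11 as the Phase I MTD.

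**On cohort 6.** A reader might infer that the plan lets ten patients be dosed above a declared MTD with nothing to prevent it. The documents do not support that. Declaring 1×10^11 the maximum tolerated dose implies that higher doses are not given, and 8.1 would class 5×10^11 as not safe. Section 7.3.4.2 stops dosing in any patient with a related DLT, boosters included, although it protects only that patient. Figures 3A and 3B are not shown and Section 3 is redacted, so a gate or a cohort 5 result may stand there. Cohort 6 appears only in this version and may have been added after cohort 5 was assessed; no readable text settles that.

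**On size.** The rates in step 5 are assumptions, and 5% to 20% lie below the protocol's own 33% limit. Those rows show how often the conflict would arise, not excess harm.

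**Conclusion.** Table 3 of the last version is wrong as written for cohorts 2 to 6: 2, 4, 8, 10 and 13 are printed where 1, 2, 4, 2 and 4 are correct, and two of the entries are impossible. It contradicts item 3, item 5 and Section 8.1. This rests only on the printed headers and arithmetic, not on anything hidden, and it needs correcting because Section 6 makes the table part of the de-escalation plan.

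The cohort 6 point is secondary and limited to the readable text. Item 6, the Summary and Section 6.2.1 set no condition on cohort 5, and the consequence of 2 or more DLT is implied rather than stated. Under assumed DLT rates of 5% to 33%, the branch in which this matters has probability 3% to 64%. It calls for a clarifying sentence. It is not evidence that no limit exists at 5×10^11.

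**What to change.** 1. **Table 3.** Restore the layout by number evaluable at a dose level, as in the preceding version: 1 for 1–3, 2 for 4–6, 3 for 7–9, 4 for 10–12, 5 for 13–15, 6 for 16–18. For the cohorts alone this gives 1, 1, 2, 4, 2, 4 (2 of 6 if cohort 1 or 2 is expanded), with 6 of 18 for cohorts 3 and 4 together and 6 of 16 for cohorts 5 and 6 together.
2. **Item 6 and the Summary.** Add one sentence: cohort 6 opens at 5×10^11 only after cohort 5 has been assessed with 0 or 1 DLT of 6. If that result is already known, stating it is enough.
3. **Consequence at 5×10^11.** State that if DLT reach 33% among all patients at this dose, cohorts 5 and 6 pooled, no further doses at this level are given, boosters included. Section 8.1 already judges by dose level, so only the consequence is new.

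The cost is protocol wording and one table. Cohort 6 might start later, because item 5 already waits 30 days after the last injection: 2 × 21 + 30 = 72 days after the last cohort 5 patient's first dose, or 70 to 86 days under the permitted 20 to 28 day intervals.
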